9.9.2 Deaths

All deaths during the study, including the Follow-up period, will be listed including the primary cause of death.

9.9.3 Clinical Laboratory Tests

All descriptive summaries of laboratory results will be based on data analyzed by the central laboratory and presented in SI units. All data will be included in by-patient data listings. Laboratory measurements identified as abnormal (i.e., outside the normal range) will also be listed separately by patient, study visit, laboratory test, unit laboratory value, normal ranges, and abnormal category (e.g. high, low, abnormal).

Clinical laboratory measurements, including chemistry and hematology, will be summarized by analysis visit up to and including the Follow-up visit as well as the last post-baseline value. Descriptive statistics will be presented for observed values as well as change from baseline for all for the Treatment and Follow-up periods. Shift from baseline CTCAE grade to worst post-baseline grade, as well as shift from baseline abnormal category (below normal, normal, above normal) to worst post-baseline category will be provided.

The CTCAE grading will be performed for all available laboratory parameters. The grading used for analysis will be based on the laboratory data only, without checking other data points that may be referenced in the CTCAE grading.

An evaluation of drug-induced serious hepatotoxicity (eDISH) plot will be generated. Additionally, a summary of the number of patients with liver test abnormalities will be provided for the worst value after first dose of study drug including ALT ($>3\times\text{ULN}$, $>5\times\text{ULN}$, $>10\times\text{ULN}$, and $>20\times\text{ULN}$), AST ($>3\times\text{ULN}$, $>5\times\text{ULN}$, $>10\times\text{ULN}$, and $>20\times\text{ULN}$), total bilirubin ($>\text{ULN}$ and $>2\times\text{ULN}$), ALP ($>1.5\times\text{ULN}$), and ALT or AST $>3\times\text{ULN}$ and total bilirubin ($>1.5\times\text{ULN}$ and $>2\times\text{ULN}$). A listing of all patients with liver test abnormalities will be provided including all laboratory values and corresponding abnormality.

9.9.4 Vital Signs

Vital sign parameter measurements, including systolic blood pressure (SBP) and diastolic blood pressure (DBP), heart rate, respiratory rate, and body temperature, will be summarized by position (seated, supine, and standing). Descriptive statistics will be presented for results, as well as change from baseline for all post-baseline analysis visits up to and including the Follow-up visit for the Treatment and Follow-up periods.

Vital signs, including SBP, DBP, heart rate, respiratory rate and body temperature will be listed.

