5.3.3 Dose Interruption and/or Discontinuation: Special Safety Events

Based on the mechanism of action of miricorilant, there is a theoretical risk of excessive GR antagonism and excessive MR antagonism. Thus far in clinical experience with miricorilant in healthy volunteers as well as in patients with AIWG, an increased incidence of excessive GR or MR antagonism has not been observed. Excessive GR antagonism could manifest as a combination of findings such as weakness, tiredness, dizziness, orthostatic hypotension, hypoglycemia, dehydration, nausea, vomiting, diarrhea, and muscle aches. Excessive MR antagonism could manifest as hyperkalemia, dehydration, and hypotension; hypotension may be seen in the absence of antihypertensive medication. These symptoms should be monitored throughout the duration of the clinical trial both during Treatment and in the Follow-up period. If excessive GR and/or MR antagonism is suspected, patients should discontinue the study medication, and administration of intravenous fluids, and intravenous or oral hydrocortisone should begin without delay. [REDACTED]

[REDACTED] Symptoms should continue to be monitored even after the last dose of study medication in the follow-up period; intravenous fluids and hydrocortisone should be administered as clinically appropriate to reverse excessive GR and MR antagonism.

At each study visit starting with the Baseline visit, patients will be evaluated for signs and symptoms of excessive GR or MR antagonism. For patients who experience symptoms, the actions outlined in [Table 2](#) should be taken.

Guidelines for temporarily interrupting and restarting and for permanently discontinuing study treatment due to other safety events (hyperkalemia; hypotension; excessive miricorilant

exposure; suspected liver injury, and significant trauma, surgery, or medical illness) are outlined in [Table 2](#).

For assessment of suspected liver injuries, baseline values for ALT, AST and total bilirubin will be the mean of all values obtained from Screening through Day 1. Please refer to the laboratory manual or individual subject laboratory report for gender- and age-specific references.

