Hypotension	
Criteria: development of hypotension while on study drug.
 
Management:
 
 • Confirm the diagnosis by office BP monitoring and orthostatic BP measurements. • Examine patient and check potassium levels. • If appropriate, advise the patient to hydrate orally with electrolyte containing hydration (e.g., Gatorade or Pedialyte). Hypotension can also be supported with intravenous hydration with isotonic fluids. • Patients who have hypotension should have any antihypertensive medications and diuretic medications discontinued as appropriate. • Interrupt miricorilant if SBP <100 mm Hg or if DBP <60 mm Hg or if orthostatic hypotension is present or if patient requires treatment with intravenous fluids. • Restart miricorilant only if hypotension is transient and reversible and not related to study medication, and after consultation with the Corcept Medical Monitor. 	
Systolic BP <100 mm Hg or diastolic BP <60 mm Hg (as confirmed by office BP measurements) or orthostasis, despite the discontinuation of antihypertensive medications and intravenous and oral hydration.

Safety Event	Criteria for Interrupting and Restarting Study Treatment and Patient Management	Criteria for Stopping Study Treatment
Hyperkalemia	Criteria: development of hyperkalemia during the study. Management: 
 • Verify hyperkalemia and normal renal function. • Obtain ECG for evaluation of hyperkalemia. • Interrupt miricorilant if hyperkalemia is severe (>6.0 mEq/L) or if renal function is impaired. • As medically indicated, initiate treatment for hyperkalemia. • Restart miricorilant only if the underlying cause of hyperkalemia is transient and correctable and after discussion with the Corcept Medical Monitor. 	Severe (>6.0 mEq/L) hyperkalemia. Confirmed ECG abnormalities including peaked T waves, shortened QT interval, ST segment depression, prolonged PR interval, flattened p wave, widened QRS, amplified R wave, or intraventricular/fascicular/bundle branch blocks. Underlying renal disease.

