6.4.1 Physical Examination and Vital Signs

Comprehensive physical examinations will be performed at Screening, Baseline, Early Termination, and Follow-up. Symptom-directed physical examinations will be performed at the other study visits. Genitourinary, rectal, and breast examinations are not required.

If clinically significant abnormalities are observed during Screening, they should be reported in the patient's medical history; if observed any time after the first dose of study drug (Day 1), they will be considered TEAEs.

Vital signs will be measured at every visit during the study, and will include resting heart rate, blood pressure, respiratory rate, and body temperature. Systolic and diastolic blood pressure will be measured after patients have been at rest (seated) for at ≥ 3 minutes. Blood pressure will be recorded in mm Hg. Heart rate (beats per minute) will be measured after the patient has been in a resting state (seated) for ≥ 3 minutes. The heart rate should be recorded over 30 seconds or longer.

Orthostatic vital signs should be performed for all patients at every visit. Heart rate and blood pressure should be taken first in a supine state at rest (lying for ≥ 3 minutes). Patient should then be instructed to stand, and heart rate and blood pressure should be repeated within 1–3 minutes after the patient has stood.

Unscheduled assessments of vital signs can be performed as necessary.

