9.9 Safety Analyses

All safety analyses will be performed in the Safety Population. All safety data will appear in by-patient data listings. Unless specified otherwise, the categorical safety analyses will include both scheduled and unscheduled visits. No comparisons between treatment groups for safety measures will be made.

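### SAP 9.9.4 neither derives the supine-to-standing change nor counts patients below the protocol's 100/60 mm Hg limits, so both must be worked out by hand from listings

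*SAP*

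**What the plan says.** **Why the readings are taken.** Protocol 5.3.3 describes the risk: "Excessive GR antagonism could manifest as a combination of findings such as weakness, tiredness, dizziness, orthostatic hypotension". It also names hypotension as a possible sign of excessive MR antagonism.

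**How they are taken.** Protocol 6.4.1 states: "Orthostatic vital signs should be performed for all patients at every visit". The supine reading comes first, after at least 3 minutes lying down. Then: "Patient should then be instructed to stand, and heart rate and blood pressure should be repeated within 1–3 minutes after the patient has stood". The two readings are therefore a pair within one patient at one visit.

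**What the protocol does with them.** Table 2 gives an interruption rule, "Interrupt miricorilant if SBP <100 mm Hg or if DBP <60 mm Hg or if orthostatic hypotension is present". Its stopping rule begins "Systolic BP <100 mm Hg or diastolic BP <60 mm Hg (as confirmed by office BP measurements) or orthostasis" and applies when the finding persists despite the listed measures. Neither rule gives a numeric fall for orthostatic hypotension or orthostasis, and neither states the body position for the 100/60 limits.

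**What the SAP does with them.** SAP 9.9.4 says the parameters "will be summarized by position (seated, supine, and standing"). It continues: "Descriptive statistics will be presented for results, as well as change from baseline for all post-baseline analysis visits". Individual values are listed. SAP 9.9 adds "No comparisons between treatment groups for safety measures will be made" and places all safety data in by-patient listings. No SAP section defines a standing-minus-supine variable or a count against the 100/60 limits.

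**The concern.** Orthostasis is a difference between two readings in one patient at one visit. A table of supine values beside a table of standing values does not contain that difference. Crossing a limit is likewise a patient-level event that can occur at any visit, and a by-visit summary does not count patients over visits.

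At stake is whether the report can show, by arm and without hand counting, how often a mechanism-based effect appeared that the visit schedule was built to detect. SAP 9.9.3 already takes the patient-level approach for liver tests: it counts patients by worst value after first dose against stated thresholds. Blood pressure has action limits in the protocol but no matching count.

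**Working it through.** Neither document states a figure on this point, so there is nothing to reproduce. The check asks what the planned outputs determine.

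**1. Mean postural shift.** If the same patients have both readings, mean(standing) − mean(supine) equals the mean of the within-patient differences. The planned tables therefore do give the average shift.

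**2. Number of patients with a large fall.** Let SD be the same in both positions and ρ the within-patient correlation. Then

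SD of postural change = SD × √(2(1 − ρ)), and

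share falling by at least c = 1 − Φ((c − mean fall) / SD of change).

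The planned tables report SD and the means but not ρ. The inputs below are assumptions and appear in neither document. The values of c show the behaviour of the formula and are not proposed definitions.

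| Mean fall, SD (mm Hg) | ρ | SD of change | Fall ≥10 | Fall ≥15 | Fall ≥20 |
|---|---|---|---|---|---|
| 5, 15 | 0.5 | 15.0 | 36.9% | 25.2% | 15.9% |
| 5, 15 | 0.7 | 11.6 | 33.3% | 19.5% | 9.8% |
| 5, 15 | 0.9 | 6.7 | 22.8% | 6.8% | 1.3% |
| 3, 12 | 0.5 | 12.0 | 28.0% | 15.9% | 7.8% |
| 3, 12 | 0.7 | 9.3 | 22.6% | 9.8% | 3.4% |
| 3, 12 | 0.9 | 5.4 | 9.6% | 1.3% | 0.1% |

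Worked case (mean fall 5, SD 15, ρ = 0.9, c = 20): 15 × √0.2 = 6.7; (20 − 5)/6.7 = 2.24; 1 − Φ(2.24) = 1.3%. Within each block of three rows the supine and standing means and SDs are identical, yet the share with a large fall differs several-fold. The positional tables do not fix the count. The table demonstrates only that; it does not estimate the effect in this trial.

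**3. Number of patients below 100/60.** SAP 9.1 includes the minimum and quartiles. A minimum below 100 mm Hg shows that at least one patient was below the limit at that visit and in that position. If the 25th percentile is at or above 100, the number lies between one and about a quarter of those measured. Neither statistic says how many different patients were ever below the limit, because patients are not linked across visits.

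**4. Unscheduled readings.** SAP 7.6 assigns unscheduled visits to windows and keeps only the visit closest to the target day. The Week 2 window runs from Day 2 to Day 22 with target Day 15. Suppose a patient has a low reading at an unscheduled visit on Day 8 and attends as planned on Day 15. The distances are |8 − 15| = 7 and |15 − 15| = 0, so Day 15 is kept. The Day 8 reading leaves the by-visit mean, quartiles and minimum alike. SAP 9.9 does include unscheduled visits in categorical safety analyses, but none is planned for vital signs.

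**The case against.** The strongest reply is that the information is in the report. All vital signs are listed by patient, so any crossing of 100/60 can be counted. The early termination described in SAP 9.8, with no patient reaching Week 12, limits the number of visits to read. The tables carry minima and quartiles as well as means.

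Other routes exist too. Protocol 6.4.1 treats clinically significant abnormalities after first dose as TEAEs. SAP 9.7 lists dose modifications with reasons, and SAP 9.9.1 lists the action taken for each AE. The Medical Monitor, a safety committee and the IDMC review safety during the study. Finally, Protocol 9.5.8 itself plans only changes from Baseline for vital signs, so the SAP delivers what the protocol promised.

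Most of this stands, and it limits the point. What remains:

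- The listings require a reader to pair positions and count by hand.
- The minima are subject to the window rule.
- The AE route depends on investigator judgement. Protocol 8.9 also asks for a unifying diagnosis in place of individual signs, so a postural fall may sit under another term.

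A further fair criticism concerns a count against 100/60. Exclusion criterion 28 sets only upper blood-pressure limits, so a patient may already be below a limit at baseline. A single low reading also does not meet the stopping rule, which requires confirmation and persistence. The table must be labelled and split accordingly.

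**Conclusion.** The gap is real and moderate. The within-patient postural change and the number of patients crossing the protocol's own limits are not derived or tabulated. They can be recovered from the listings only by hand, and the by-visit tables can omit low readings from unscheduled visits. This rests on the text of both documents and not on any assumed rate or SD. Its size in patients cannot be stated from the documents.

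Four stronger readings are tempting and are not supported:

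- **That the orthostatic signal goes unreported, or that the trial could never state the count.** The by-patient listings in SAP 9.9 and 9.9.4 contain the readings.
- **That the SAP plans nothing beyond means.** SAP 9.1 specifies median, quartiles, minimum and maximum.
- **That the SAP departs from the protocol.** Protocol 9.5.8 plans no postural analysis either, so the gap is in both documents.
- **That the early termination concerned blood pressure.** SAP 9.8 refers to safety observations without saying which.

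**What to change.** Add to SAP 9.9.4, as descriptive output only, in keeping with SAP 9.9:

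- **(a)** Derive standing minus supine SBP, DBP and heart rate per patient per visit. Summarise it by arm and visit, with its change from baseline.
- **(b)** Tabulate by arm the number of patients with any post-baseline SBP <100 or DBP <60 mm Hg. Include unscheduled visits, and show the result by position and by whether the patient was already below the limit at baseline. Label it as a count of readings below the limit, not of patients who met a Table 2 rule.
- **(c)** Count orthostatic hypotension or orthostasis only after the sponsor has settled a definition in the documents. Table 2 uses both terms without a numeric one, and none is proposed here.

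Item (b) follows the worst-value approach of SAP 9.9.3. Items (a) and (b) need no new data and no new threshold. The cost is one derived variable and one extra table.

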9.9.5 Electrocardiograms

Twelve-lead ECG interval parameters will be summarized. Descriptive statistics will be presented for observed values as well as change from baseline for all post-baseline analysis visits up to and including the Follow-up visit for the Treatment and Follow-up periods using the average of the triplicate readings per patient per visit.

Twelve-lead ECG results will be classified as “normal”, “abnormal not clinically significant”, and “abnormal clinically significant” on the eCRF. A listing of ECG results will be provided including visit, date, and interpretation results.

9.9.6 Physical Examination

Results of the physical examination will be presented in patient data listings by study visit and body system. A listing of abnormal physical exam findings by visit and body system will be provided. The description of the abnormal finding and indication if the finding was clinically significant or not will be displayed.

9.9.7 Pregnancy Tests

Results of the pregnancy tests will be presented in patient data listings by study visit.

9.10 Subgroup Analyses

No subgroup analyses will be performed.

9.11 COVID-19 Infection

Information regarding visits that are affected by coronavirus disease of 2019 (COVID-19) pandemic are being collected on the eCRF. A listing of visits that are affected by COVID-19

pandemic will be provided. Additionally, a listing of protocol deviations associated with COVID-19 and an AE listing of patients with a positive diagnosis of COVID-19 infection will be provided. Any additional analyses determined to be appropriate for patients impacted by the COVID-19 pandemic will be performed as deemed necessary.

10 CHANGES FROM PROTOCOL IN STUDY CONDUCT OR STATISTICAL ANALYSIS PLAN

The SAP supersedes the statistical methods described in the clinical study protocol. Analysis methods that summarize and evaluate study efficacy endpoints for statistical significance will be implemented as described in the SAP. Changes from the protocol statistical analysis include:

- Removal of the Modified Intent-to-Treat, Efficacy Evaluable, and PK populations.
- Removal of PK analysis including calculation of the PK parameters of miricorilant estimated by noncompartmental methods, summary of PK parameters, and plots of plasma concentrations of miricorilant. A PK analysis plan will not be prepared. Any reported PK data will be listed as observed.
- Removal of analyses of exploratory endpoints in patients with diabetes or high blood pressure.
- The sample size at the time of study termination does not support formal comparisons of the treatment groups, and therefore, no efficacy analyses specified in the protocol will be performed.

12 APPENDIX

12.1 Imputation of Missing/Partially Missing Dates

For adverse events with a partial date, available date parts (year, month, and day) of the partial date will be compared with the corresponding date components of the start date and end date of the treatment-emergent period to determine if the event is treatment emergent. The following rules will be applied to impute partial dates for adverse events.

If start date of an adverse event is partially missing, following imputation rules will be applied:

- If both Month and Day are missing and Year = Year of treatment start date, then set to treatment start date.
- If both Month and Day are missing and Year \neq Year of treatment start date, then set to January 1.
- If Day is missing and Month and Year = Month and Year of treatment start date, then set to treatment start date.
- If Day is missing and Month and Year \neq Month and Year of treatment start date, then set to first of the month.
- If start date is completely missing, set to treatment start date as long as adverse event end date is not prior to treatment start date.

If end date of an adverse event is partially missing, following imputation rules will be applied:

- If both Month and Day are missing, then set to December 31.
- If only Day is missing, then set to last day of the month.
- If end date is completely missing, do not impute.

When the start date or end date of a medication is partially missing, the date will be imputed to determine whether the medication is prior or concomitant (or both). The following rules will be applied to impute partial dates for medications:

If start date of a medication is partially missing, following imputation rules will be applied:

- If both Month and Day are missing, then set to January 1.
- If only Day is missing, then set to the first.

If end date of a medication is partially missing, following imputation rules will be applied:

- If both Month and Day are missing, then set to December 31.
- If only Day is missing, then set to last day of the month.

If start date or end date of a medication is completely missing, no imputation is applied.

Certificate Of Completion

Envelope Id: E5A279FADB8040908649F2C5560E5C25
 Subject: Please DocuSign: CORT118335_860_SAP_v1_0_FINAL.docx.pdf
 Source Envelope:
 Document Pages: 27
 Certificate Pages: 5
 AutoNav: Enabled
 EnvelopeD Stamping: Disabled
 Time Zone: (UTC-08:00) Pacific Time (US & Canada)

Status: Completed

Envelope Originator:

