6.4.4 Adverse Events

Details on definitions and reporting of AEs are provided in Section 8.

All AEs will be recorded from the time of signing of the ICF until 28 days after the last dose of study drug. Patients should be monitored for AEs and AEs assessed for expectedness consistent with the current IB for miricorilant. To help characterize any possible relationships between drug exposure and the clinical event, when an SAE occurs, ACTH, cortisol, and aldosterone levels should be assessed as close to the time of the event as possible and a PK sample may be drawn at the discretion of the Investigator.

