7.1 Definitions

Study day for efficacy will be calculated in reference to the date of first dose of miricorilant or placebo (Study Day 1). For assessments conducted on or after the first dose date, study day is calculated as (assessment date – first dose date + 1). For assessments conducted before the first dose date, study day is calculated as (assessment date – first dose date). There is no study Day 0.

Treatment-emergent period: The treatment-emergent period is defined as the period of time from the date of the first dose of study drug (inclusive) through 28 days after the last dose of study drug. The treatment-emergent period will be used in the summaries of TEAEs.

Baseline will be the assessment on the Day 1 visit if non-missing, or the last non-missing assessment prior to first dose of study drug if Day 1 visit is missing.

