9.9.1 Adverse Events

TEAEs are defined as those AEs with onset on or after the first dose date of study drug or existing events that worsened after the first dose during the study and up to and including 28 days after the last dose of study drug, per protocol. Any AEs reported more than 28 days after the last dose of study drug will be considered post-treatment AEs.

Events reported with a partial onset date (e.g., month and year are reported but the day is missing) will be considered to be treatment-emergent, as appropriate, if it cannot be confirmed that the event onset was prior to the first dose of study drug based on the available date entries.

Summaries that are displayed by system organ class (SOC) and preferred terms (PT) will be ordered by alphabetical order of SOC and by descending total incidence PT nested within each system organ class. Summaries displayed by PT only will be ordered by descending total incidence of PT.

Tabular summaries with numbers and percentages of patients that have the following adverse events will be provided:

- Overview of TEAEs
- Summary of TEAEs
- Summary of TEAEs related to study drug (defined as possibly related, probably related, or related)
- Summary of TEAEs leading to discontinuation
- Summary of Serious TEAEs
- Summary of Serious TEAEs related to study drug
- Summary of Serious TEAEs leading to discontinuation
- Summary of TEAEs with fatal outcome
- Summary of TEAEs with Grade 3 or higher

All above summaries will be presented by PT, and by PT nested within SOC. Also, summaries by maximum severity will be provided for TEAEs and Serious TEAEs.

All AEs, whether treatment-emergent or not, will be listed by treatment arm and individual patient, including dates of onset and resolution and associated study day, duration, serious, NCI-CTCAE grade (CTCAE v.5.0), action taken, outcome, and relationship to study drug. Serious TEAEs and TEAEs leading to discontinuation will also be listed separately.

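### SAP 12.1 moves some partial AE start dates to the first-dose date without the end-date check it applies to wholly missing starts, so a resolved screening event can start after it ended and may be counted as a TEAE

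*SAP*

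**What the plan says.** SAP 12.1 has three rules that can set an AE start to the treatment start date:

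- Day missing, month and year matching first dose: "If Day is missing and Month and Year = Month and Year of treatment start date, then set to treatment start date".
- Month and day missing, year matching first dose: "If both Month and Day are missing and Year = Year of treatment start date, then set to treatment start date".
- Start wholly missing: "set to treatment start date as long as adverse event end date is not prior to treatment start date".

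Only the third depends on the end date. The same section says how treatment emergence is decided for a partial date: its known parts "will be compared with the corresponding date components of the start date and end date of the treatment-emergent period". SAP 7.1 defines that period as running "from the date of the first dose of study drug (inclusive) through 28 days after the last dose of study drug".

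SAP 9.9.1 has its own rule for partial onset dates. Where appropriate, the event is classed as treatment-emergent on one condition: "if it cannot be confirmed that the event onset was prior to the first dose of study drug based on the available date entries". Neither section refers to the other.

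Protocol 6.4.4 fixes the collection period: "All AEs will be recorded from the time of signing of the ICF until 28 days after the last dose of study drug". Screening runs from Day -42 to Day -1 (Protocol 7.1).

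**The concern.** A known pre-dose end date blocks the move to first dose when nothing is known about the start, but not when the month or year is known. Having more information about the start removes the safeguard. The condition beside these rules shows that its principle was already accepted, so this looks like an omission.

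The cases can arise because AEs are recorded throughout screening, often in the same month or year as first dose.

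Two things are at stake. The imputed dates can be impossible, with a start later than a recorded end. Treatment-emergent status can also be wrong. The second matters more here because the study was terminated for safety observations and its efficacy analyses are descriptive only (SAP 9.8), which leaves the TEAE tables as a main output.

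**Working it through.** The plan gives no figure to reproduce, so the check applies the 12.1 rules literally to test cases.

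**Inputs.** The start and end rules are from SAP 12.1. A partial end date goes to the last day of the month, or to 31 December. The treatment-emergent period is from SAP 7.1. The first dose of 20 March 2021 is illustrative.

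| Case | Recorded start | Recorded end | End used | Start under 12.1 | Start after end? | Start in treatment-emergent period? |
|---|---|---|---|---|---|---|
| A | Mar 2021, day missing | 10 Mar | 10 Mar | 20 Mar | Yes | Yes |
| B | 2021 only | 25 Feb | 25 Feb | 20 Mar | Yes | Yes |
| C | 2021 only | Feb, day missing | 28 Feb | 20 Mar | Yes | Yes |
| D | Mar 2021, day missing | Mar, day missing | 31 Mar | 20 Mar | No | Yes |
| E | Wholly missing | 10 Mar | 10 Mar | Not set to first dose | No | No |
| F | Mar 2021, day missing | 25 Mar | 25 Mar | 20 Mar | No | Yes |

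A and E have the same end date and differ only in how much of the start is known. The safeguard works in E and is absent in A.

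**Generality.** Suppose first dose is on day d of a 31-day month, and an event began and ended earlier that month with its onset day missing. There are d(d-1)/2 possible onset/end pairs. Summed over d = 1 to 31 this is 32 × 31 × 30 / 6 = 4,960. All 4,960 give a start after the end, because the end is at most d-1 and the imputed start is d.

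**Treatment-emergent status of A, B and C.**

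- Under 12.1 alone, the imputed start is the first-dose date, which is included in the period, so the events could be counted as TEAEs.
- Under 9.9.1, with the end date treated as an available date entry, earlier onset is confirmed and they are not TEAEs.
- Under 9.9.1, with only the onset parts treated as available date entries, earlier onset is not confirmed and they are TEAEs.

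In all three readings the imputed start still falls after the end.

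**Duration.** SAP 9.9.1 lists duration but gives no formula. Assuming end minus start plus 1, and assuming imputed dates are used, A gives 10 - 20 + 1 = -9 days. An end on the day before dosing gives 19 - 20 + 1 = 0, so the duration is never positive.

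**Effect on a table.** The enrolled number is not in the documents. Assuming 10 to 15 patients per arm, one false TEAE adds 1/15 = 6.7 to 1/10 = 10 percentage points, provided the patient is not already counted in that row. At the planned 40 per arm it would be 1/40 = 2.5 points.

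**With the end-date condition added.** A, B and C are no longer moved to first dose and are not treatment-emergent. D and F are unchanged. The fallback start needs a floor: 42 days before 20 March is 6 February, so 1 January in B and C would precede any possible consent. Assuming consent on 6 February, the later of consent and the earliest compatible date is 1 March for A and 6 February for B and C. Each is before its end date.

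**The case against.** The strongest reply is SAP 9.9.1. It is the specific provision for partial onset dates, and an end date before first dose is naturally a date entry that confirms earlier onset. A reader might infer from 12.1 that these events certainly become TEAEs. The documents do not support that, because 9.9.1 can be read to exclude them. What remains is that 12.1 makes its own determination from the parts of the partial date, names no end date for that purpose, and does not defer to 9.9.1. A programmer following 12.1 could reach the other answer.

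A reader might also infer that the AE listing will show negative durations. The SAP does not say that listings print imputed dates or compute duration from them, so this is conditional.

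The scope is narrow. It would be wrong to say that every screening event in the first-dose month or year is affected. The event must also have a partial start and an end known to precede first dose. Onset and resolution dates are required for each AE (Protocol 8.9), missing data are queried with sites (Protocol 11.1), and analysis follows query resolution (SAP 8.2). These steps make such cases uncommon but do not rule them out, since the SAP itself provides for partial dates.

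SAP 7.5 says AE dates are imputed conservatively, and SAP 9.9 plans no between-group safety comparisons. Conservatism is a reason to count an event when timing is uncertain. It does not justify overriding a recorded end date that settles the matter. The absence of comparisons lowers the stakes but does not make a listed date or an incidence correct.

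**Conclusion.** The gap in 12.1 is real. For an AE known to have ended before first dose, both partial-date rules put the imputed start after the end and inside the treatment-emergent period. This follows directly from the text.

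Misclassification as a TEAE is a risk arising from two unreconciled sections, not a certain result. It depends on 12.1 being applied literally, or on 9.9.1 being read as limited to the onset parts. A non-positive duration depends on imputed dates being used in the listing.

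The number of affected events is unknown and may be zero. The 6.7 to 10 point effect rests on the assumed 10 to 15 patients per arm and on one such event occurring. The point is worth correcting because safety is a main output and the correction is short.

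**What to change.** In SAP 12.1:

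1. Apply the existing condition to both partial-date rules: set the start to the treatment start date only if the AE end date is missing or not before treatment start. Evaluate this on the end date after the end-date rules have been applied. Those rules give the latest possible date, so only an end certain to precede first dose blocks the move.
2. Otherwise, set the start to the later of the consent date and the earliest date compatible with the known parts, and classify the event as not treatment-emergent. The consent floor is needed because illness present before consent is medical history, not an AE (Protocol 8.3).
3. State that 9.9.1, using the AE end date, governs classification.

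The cost is a small programming change: the condition, the fallback with its consent-date input, and a cross-reference. Events ending on or after first dose, or with no end date, are treated as now. If the SAP is already final, the change can be documented in the CSR, as SAP Section 1 provides.
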